3.2 Exclusion Criteria

Patients who meet any of the following criteria will be excluded from study entry:

1. Previous therapy or known intolerance/hypersensitivity with any approved or investigational mTOR inhibitor (e.g., temsirolimus, everolimus, sirolimus).
2. Patients who are ≤ 21 days after their most recent chemotherapy and have not recovered from side effects.
3. Use of an investigational drug ≤ 21 days or 5 half-lives (whichever is shorter) prior to the first dose of everolimus. For investigational drugs for which 5 half-lives is ≤ 21 days, a minimum of 10 days between termination of the investigational drug and administration of everolimus is required.
4. Wide field radiotherapy (including therapeutic radioisotopes such as strontium 89) administered ≤ 28 days or limited field radiation for palliation ≤ 7 days for metastatic disease prior to first dose of everolimus or has not recovered from side effects of such therapy.

CONFIDENTIAL

STUDY DRUG(S): EVEROLIMUS
FINAL PROTOCOL DATE: 19 JUNE 2014

SCRI INNOVATIONS STUDY NUMBER: BRE 212
VERSION 1.0

5. Previously untreated brain metastases. Patients who have received radiation or surgery for brain metastases are eligible if there is no evidence of central nervous system (CNS) disease progression, and at least 2 weeks have elapsed since treatment. Patients are not permitted to receive enzyme inducing anti-epileptic drugs (EIAEDs) during the study and should not be receiving chronic corticosteroid therapy for CNS metastases.
6. Cardiac disease, including: congestive heart failure (CHF) > Class II per New York Heart Association (NYHA, Appendix B) classification; unstable angina (anginal symptoms at rest) or new-onset angina (i.e., began within the last 3 months), or myocardial infarction within the past 6 months; symptomatic CHF, unstable angina pectoris, or cardiac ventricular arrhythmias requiring anti-arrhythmic therapy.
7. Patients who have any severe and/or uncontrolled medical conditions or other conditions that could affect their participation such as:
 - Severe impaired lung functions as defined as spirometry and diffusing capacity of the lung for carbon monoxide (DLCO) that is 50% of the normal predicted value and/or O₂ saturation that is 88% or less at rest on room air
 - Uncontrolled diabetes as defined by HbA1c >8% despite adequate therapy.
 - Liver disease such as cirrhosis or severe hepatic impairment (Child-Pugh class C)
 - Any history of a bleeding diathesis.

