8. Impairment of gastrointestinal function or gastrointestinal (GI) disease that may significantly alter absorption of everolimus (e.g., ulcerative disease, uncontrolled nausea, vomiting, diarrhea, malabsorption syndrome, or small bowel resection).
9. Patients with known active hepatitis B (HBV) or hepatitis C (HCV) infection. Patients with risk factors for hepatitis (See Section 7.1) must have HBV DNA and HCV RNA testing by PCR, and are ineligible if these tests are positive.
10. Concurrent use of strong CYP3A4 inhibitors or inducers from 72 hours prior to initiation of study treatment until the end of treatment with everolimus (See Section 5.5).
11. Chronic treatment with systemic steroids or other immunosuppressive agents. Note: Topical or inhaled corticosteroids are allowed.
12. Patients receiving immunization with attenuated live vaccines within 1 week of study entry or during study period (See Section 5.4).

CONFIDENTIAL

STUDY DRUG(S): EVEROLIMUS
FINAL PROTOCOL DATE: 19 JUNE 2014

SCRI INNOVATIONS STUDY NUMBER: BRE 212
VERSION 1.0

13. Pregnant or lactating women or women of childbearing potential without a negative serum pregnancy test, ≤ 7 days prior to date of first treatment, regardless of the method of contraception used.
14. Patients with known human immunodeficiency virus (HIV) seropositivity.
15. History of other malignancy ≤ 5 years of study entry which could affect compliance with the protocol or interpretation of results. Note: History of curatively treated basal or squamous cell carcinoma of the skin or in situ carcinoma of the cervix, or ductal carcinoma in situ (DCIS) of the breast treated with lumpectomy alone with curative intent, are generally eligible.
16. Significant concurrent, uncontrolled medical condition which, in the opinion of the investigator, may interfere with patient participation in the study.

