3.3 Discontinuation from Study Treatment

Patients will be discontinued from study treatment for any of the following reasons:

- Disease progression.
- Irreversible or intolerable toxicity or abnormal laboratory values.
- Patient requests to withdraw from the study and discontinue treatment.
- Inability of the patient to comply with study requirements.
- Conditions requiring therapeutic intervention not permitted by the protocol.
- Intercurrent illness (this will be at the investigator's discretion).
- Non-compliance or lost to follow-up.

After discontinuation from protocol treatment, patients must be followed for AEs for 30 calendar days after their last dose of study drug. All new AEs occurring during this period must be reported and followed until resolution, unless, in the opinion of the investigator, these values are not likely to improve because of the underlying disease. In this case, the investigator must record his or her reasoning for this decision in the patients' medical records and as a comment on the electronic Case Report Form (eCRF).

All patients who have Grade 3 or 4 laboratory abnormalities (Common Terminology Criteria for Adverse Events [CTCAE] v4.0 (<http://evs.nci.nih.gov/ftp1/CTCAE/CTCAE>) at the time of discontinuation must be followed until the laboratory values have returned to Grade 1 or 2, unless it is, in the opinion of the investigator, not likely that these values are to improve. In this case, the investigator must record his or her reasoning for making this decision in the patients' medical records and as a comment on the CRF.

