5.5 CYP3A4 and/or PgP Inhibitors/Inducers/Substrates

Everolimus is metabolized by CYP3A4 in the liver and to some extent in the intestinal wall. Therefore, the following are recommended:

- Co-administration with strong inhibitors of CYP3A4 (e.g., ketoconazole, itraconazole, ritonavir) or P-glycoprotein (PgP) inhibitor should be avoided.
- Co-administration with moderate CYP3A4 inhibitors (e.g. erythromycin, fluconazole) or PgP inhibitors should be used with caution. If a patient requires co-administration of moderate CYP3A4 inhibitors or PgP inhibitors, reduce the dose of everolimus by approximately 50%. Additional dose reductions to every other day may be required to manage toxicities. If the inhibitor is discontinued, the everolimus dose should be returned to the dose used prior to initiation of the moderate CYP3A4/PgP inhibitor after a washout period of 2 to 3 days.
- Grapefruit or citrus juices affect P450 and PgP activity; therefore, concomitant use should be avoided.
- If patients require co-administration of a strong CYP3A4 inducer, consider doubling the daily dose of everolimus (based on pharmacokinetic data), using increments of 5 mg or less. This dose of everolimus is predicted to adjust the AUC to the range observed without inducers. However, there are no clinical data with this dose adjustment in patients receiving strong CYP3A4 inducers. If the strong inducer is discontinued, consider a washout period of at least 3 to 5 days (reasonable time for significant enzyme de-induction), before the everolimus dose is returned to the dose used prior to initiation of the strong CYP3A4 inducer.
- This dose adjustment of everolimus is intended to achieve similar AUC to the range observed without inducers. However, there are no clinical data with this dose adjustment in patients receiving strong CYP3A4 inducers. If the strong inducer is discontinued the everolimus dose should be returned to the dose used prior to initiation of the strong CYP3A4/PgP inducer.
- Oral contraceptives in preclinical and clinical data have shown everolimus to have CYP3A4 inhibitory activity rather than induction activity; induction of metabolism of contraceptive hormones by everolimus is unlikely. Consequently, administration of everolimus should not reduce the efficacy of oral contraceptives.

Refer to the listing of relevant inducers and inhibitors of CYP3A4 and the list of relevant substrates, inducers and inhibitors of PgP in Appendix E.

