1. For mild toxicity (Grade 1), use conservative measures such as non-alcoholic mouth wash or salt water (0.9%) mouth wash several times a day until resolution.
2. For more severe toxicity (Grade 2 in which case patients have pain but are able to maintain adequate oral alimentation, or Grade 3 in which case patients cannot maintain adequate oral alimentation), the suggested treatments are topical analgesic mouth

CONFIDENTIAL

STUDY DRUG(S): EVEROLIMUS
FINAL PROTOCOL DATE: 19 JUNE 2014

SCRI INNOVATIONS STUDY NUMBER: BRE 212
VERSION 1.0

treatments (i.e., local anesthetics such as, benzocaine, butyl aminobenzoate, tetracaine hydrochloride, menthol, or phenol) with or without topical corticosteroids, such as triamcinolone oral paste 0.1% (Kenalog in Orabase®).

3. Agents containing alcohol, hydrogen peroxide, iodine, and thyme derivatives may tend to worsen mouth ulcers. It is preferable to avoid these agents.
4. Antifungal agents should be avoided unless a fungal infection is diagnosed. In particular, systemic imidazole antifungal agents (ketoconazole, fluconazole, itraconazole, etc.) should be avoided in all patients due to their strong inhibition of everolimus metabolism, therefore leading to higher everolimus exposures. Therefore, topical antifungal agents are preferred if an infection is diagnosed.

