Appendix F: Clinically Relevant Drug Interactions of CYP3A and PgP

Clinically relevant drug interactions: inducers, and inhibitors of isoenzyme CYP3A

Inducers

Strong inducers:

avasimibe, carbamazepine, mitotane, phenobarbital, phenytoin, rifabutin, rifampin (rifampicin), St. John's wort, (hypericum perforatum)

Moderate inducers:

bosentan, efavirenz, etravirine, genistein, modafinil, naftillin, ritonavir, [talviraline], thioridazine, tipranavir

Weak inducers:

amprenavir, aprepitant, armodafinil (R-modafinil), bexarotene, clobazam, danshen, dexamethasone, Echinacea, garlic (allium sativum), gingko (ginkgo biloba), glycyrrhizin, methylprednisolone, nevirapine, oxcarbazepine, pioglitazone, prednisone, [pleconaril], primidone, raltegravir, rufinamide, sorafenib, telaprevir, terbinafine,

Inhibitors

Strong inhibitors:

boceprevir, clarithromycin, cobicistat, conivaptan, elvitegravir, indinavir, itraconazole, ketoconazole, lopinavir, mibefradil, nefazodone, neflifinavir, posaconazole (Krishna et al 2009), ritonavir, saquinavir, telaprevir, telithromycin, tipranavir, troleandomycin, voriconazole

Moderate inhibitors:

Amprenavir, aprepitant, atazanavir, casopitant, cimetidine, ciprofloxacin, cyclosporine, darunavir, diltiazem, dronedarone, erythromycin, fluconazole, fosamprenavir, grapefruit juice (citrus parasida fruit juice), imatinib, schisandra sphenanthera, tofisopam, verapam

CONFIDENTIAL

STUDY DRUG(S): EVEROLIMUS
FINAL PROTOCOL DATE: 19 JUNE 2014

SCRI INNOVATIONS STUDY NUMBER: BRE 212
VERSION 1.0

Clinically relevant drug interactions: substrates, inducers, inhibitors of PgP and PgP/CYP3A dual inhibitors

Substrates

colchicine, digoxin, fexofenadine, indinavir, paclitaxel, talinolol, topotecan, vincristine, everolimus

Inducers

rifampin, St John's wort

PgP Inhibitors and PgP/CYP3A Dual Inhibitors

amiodarone, azithromycin, captopril, carvedilol, clarithromycin, conivaptan, diltiazem, dronedarone, elacridar, erythromycin, felodipine, fexofenadine, fluvoxamine, ginkgo (ginkgo biloba), indinavir, itraconazole, lopinavir, mibepradil, milk thistle (silybum marianum), nelfinavir, nifedipine, nitrendipine, paroxetine, quercetin, quinidine, ranolazine, rifampin, ritonavir, saquinavir, Schisandra chinensis, St John's wort (hypericum perforatum), talinolol, Telaprevir, telmisartan, ticagrelor, tipranavir, tolvaptan, valsartan, verapamil

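### Exclusion criterion 10 bars strong CYP3A4 inducers until everolimus ends, but Section 5.5 provides for their use with a dose adjustment; fluconazole guidance also conflicts

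*Protocol*

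**What the plan says.** **Strong inducers.** Protocol Section 3.2, exclusion 10, repeated in the Synopsis, excludes "Concurrent use of strong CYP3A4 inhibitors or inducers from 72 hours prior to initiation of study treatment until the end of treatment with everolimus" and cites Section 5.5. The fourth bullet of Section 5.5 reads: "If patients require co-administration of a strong CYP3A4 inducer, consider doubling the daily dose of everolimus". It adds that the adjustment rests on pharmacokinetic data, is made in steps no larger than 5 mg, and has no clinical data behind it. Section 3.3 lists among the reasons for stopping study treatment: "Conditions requiring therapeutic intervention not permitted by the protocol".

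**Enzyme-inducing anti-epileptics.** Exclusion 5, the criterion on brain metastases, states: "Patients are not permitted to receive enzyme inducing anti-epileptic drugs (EIAEDs) during the study". Appendix F places carbamazepine, phenobarbital and phenytoin among the strong CYP3A inducers.

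**Fluconazole.** The second bullet of Section 5.5 says: "Co-administration with moderate CYP3A4 inhibitors (e.g. erythromycin, fluconazole) or PgP inhibitors should be used with caution". Where such a drug is required, it calls for a reduction of about 50% in the everolimus dose. Appendix F also lists fluconazole as moderate. Section 6.2.6, item 4, names fluconazole with ketoconazole and itraconazole as agents that "should be avoided in all patients due to their strong inhibition of everolimus metabolism".

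**PgP inhibitors.** In the first bullet of Section 5.5, co-administration with a strong CYP3A4 inhibitor "or P-glycoprotein (PgP) inhibitor should be avoided". The second bullet allows PgP inhibitors with caution and a reduced dose.

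**The concern.** A site with a patient who comes to need a strong inducer during treatment has two instructions with different consequences. Exclusion 10 reads as a prohibition and leads, through Section 3.3, to stopping study treatment. Section 5.5 reads as permission with a dose adjustment. Because exclusion 10 sends the reader to Section 5.5, the conflict cannot be put down to an unrelated section that sites would not consult.

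The stakes are patient safety and consistent handling across about 9 sites. Whether a patient stays on everolimus, and at what dose, could depend on which section the site reads. Fluconazole raises the same kind of question on a smaller scale. It could plausibly come up, because stomatitis is an expected everolimus toxicity and Section 6.2.6 discusses antifungal treatment there.

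**Working it through.** No figure in the plan depends on this point, so the check is a comparison of the current texts.

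| Situation | One passage | Another passage |
|---|---|---|
| Strong CYP3A4 inducer needed on study | Exclusion 10: barred until everolimus ends; Section 3.3 then points to stopping treatment | Section 5.5, fourth bullet: continue and consider doubling the dose |
| Carbamazepine, phenobarbital or phenytoin needed | Exclusion 5: enzyme-inducing anti-epileptics barred during the study | Appendix F: strong inducers, so within the Section 5.5 dose rule |
| Systemic fluconazole needed | Section 6.2.6, item 4: avoid in every patient, strong inhibition | Section 5.5 and Appendix F: moderate; Section 5.5 allows caution and about a 50% reduction |
| PgP inhibitor needed | Section 5.5, first bullet: avoid | Section 5.5, second bullet: caution and about a 50% reduction |
| Strong inducer stopped | Section 5.5, fourth bullet: consider at least 3 to 5 days before returning to the previous dose | Section 5.5, fifth bullet: return to the previous dose, no washout mentioned |

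1. **Can exclusion 10 be read as applying at entry only?** No. It sits under a heading about study entry, but its own time window runs to the end of everolimus treatment.

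2. **Does Section 5.5 repeat the ban?** Only for inhibitors. Its first bullet says strong inhibitors should be avoided, which is softer than exclusion 10 but points the same way. No bullet says that strong inducers are not allowed.

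3. **What follows for one patient?** If a drug barred by exclusion 10 counts as not permitted under Section 3.3, the outcomes on 10 mg daily are discontinuation or, with doubling, 2 × 10 mg = 20 mg daily. Both are readings of the text, and neither is endorsed here.

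4. **Fluconazole.** On the same starting dose, the range runs from not giving fluconazole to giving it with everolimus at about 0.5 × 10 mg = 5 mg daily. The label also differs: the wording of Section 6.2.6 groups fluconazole with strong inhibitors, while Section 5.5 and Appendix F call it moderate. The label matters because exclusion 10 applies to strong inhibitors.

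5. **PgP inhibitors.** Appendix F gives one list, not graded by strength, so a site cannot use it to sort drugs between the first two bullets. Rifampin and St John's wort appear both as strong CYP3A inducers and as PgP inhibitors, so Section 5.5 can be read as pointing to opposite dose changes for them.

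6. **Cross-reference.** Section 5.5 sends sites to Appendix E for the drug lists. Appendix E contains RECIST; the lists are in Appendix F.

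**The case against.** The best defence is that exclusion 10 sets the rule, while Section 5.5, framed as recommendations, supplies a fallback for a patient whose need for an inducer cannot be avoided. The dose rule also has a stated aim, which is to bring everolimus exposure back to the range seen without an inducer. That aim should be acknowledged. But no passage describes Section 5.5 as an exception to exclusion 10, and Section 3.3 has no carve-out for it. The conflict stands.

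Several stronger readings are tempting and are not supported:

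- **That a doubled dose breaches Table 1.** Table 1 concerns toxicity and is introduced as a set of dose reductions. It does not claim to list every permitted dose, so an interaction adjustment outside it is not a contradiction.
- **That the PgP bullets are flatly opposed.** They can be read in parallel, with strong inhibitors avoided and moderate ones used with caution. The last sentence of the second bullet places the word moderate before CYP3A4 and PgP together. What remains is ambiguity, because Appendix F does not grade PgP inhibitors.
- **That the washout bullets give opposite orders.** One suggests considering a washout and the next is silent. This is redundant drafting that should be aligned.
- **That the fluconazole passages demand opposite actions.** Avoidance can be a default and a reduced everolimus dose a fallback when the drug is required. Section 6.2.1 also has everolimus discontinued for invasive systemic fungal infection, so part of that scenario involves no co-administration. The difference in label, and the reference to all patients, remain.
- **That the PFS result is materially biased.** A route exists: the PFS table in SAP Section 4 censors at the last evaluable tumor assessment when treatment stops for a non-event reason. The documents give no count of such patients, so no effect on median PFS can be shown.

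Reach may well be small. Exclusion 5 separately bars some of these drugs, and Section 5.4 asks patients to consult the investigator before taking any additional medication.

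**Conclusion.** The point holds as an internal inconsistency in the protocol. The main conflict, on strong inducers, is plain on the text and is not reconciled anywhere. Fluconazole is a genuine but lesser inconsistency. The PgP wording, the two inducer bullets and the appendix reference are minor.

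Its size is qualitative: for one patient, stopping treatment versus continuing on an adjusted dose. The number of patients affected is not stated and cannot be derived.

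The conclusion rests on two readings: that exclusion 10 binds during treatment, as its time window says, and that a drug it bars counts as a non-permitted intervention under Section 3.3. The anti-epileptic point is supporting evidence. If that sentence in exclusion 5 were limited to patients with treated brain metastases, exclusion 10 would still produce the same conflict for those drugs.

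**What to change.** The sponsor should reconcile exclusions 5 and 10 (including the Synopsis copies), Section 3.3, Section 5.5, Section 6.2.6 item 4 and Appendix F so that strong inducers, fluconazole and PgP inhibitors each carry one consistent instruction. If Section 5.5 is meant as an exception to exclusion 10, the text should say so and state how Section 3.3 then applies; if it is not, the passages should be aligned.

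The two consecutive inducer bullets should be reconciled by a deliberate decision on the washout. Deleting one of them as a duplicate would settle that question silently. The Section 5.5 references to Appendix E should point to Appendix F.

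Which rule or dose applies is for the sponsor to decide. The cost is protocol wording, handled under Section 14.1, and a memo to sites. Sample size, endpoints and analyses are unaffected.

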6. DOSE MODIFICATIONS

All toxicities will be graded utilizing the NCI CTCAE v 4.0 (<http://evs.nci.nih.gov/ftp1/CTCAE/CTCAE>). If toxicity occurs, the toxicity will be graded, and appropriate supportive care treatment will be administered to decrease the signs and symptoms thereof. Dose adjustments will be based on the organ system exhibiting the greatest degree of toxicity.

Adverse events most frequently observed with everolimus are rash, stomatitis/oral mucositis, non-infectious pneumonitis, fatigue, headache, anorexia, nausea, vomiting, diarrhea, and infections. Overall, the most frequently observed laboratory abnormalities include neutropenia, thrombocytopenia, hyperglycemia, hypercholesterolemia, and/or hypertriglyceridemia. The majority of these AEs have been of mild to moderate severity (NCI CTCAE Grade 1-2).

The dose level reductions for everolimus to be used in this study are shown in Table 1.

If everolimus is interrupted for any reason, and the patient has no toxicity related to anti-estrogen therapy, the patient should continue anti-estrogen therapy per schedule. If the patient discontinues everolimus for any reason, they should continue to receive anti-estrogen therapy if patient is deriving clinical benefit from the therapy.

Table 1 Everolimus Dose Level for Toxicity

Dose Level	Everolimus
Starting Dose	10 mg daily
Dose Level -1	5 mg daily
Dose Level -2	5 mg every other day

No more than 2 dose reductions for everolimus are permitted. Patients who need an additional dose reduction will be required to discontinue everolimus.

Table 2 lists the dosing guidelines for everolimus-related hematologic toxicities, Table 3 and Table 4 list the dosing guidelines for everolimus-related non-hematologic toxicities.

CONFIDENTIAL

STUDY DRUG(S): EVEROLIMUS
FINAL PROTOCOL DATE: 19 JUNE 2014

SCRI INNOVATIONS STUDY NUMBER: BRE 212
VERSION 1.0

6.1 Dose Modifications Due to Hematologic Toxicity

Dose modifications on Day 1 of each cycle will be based on blood counts determined on the day of scheduled treatment. Nadir blood counts will not be used to determine dose modifications. Treatment on Day 1 of any cycle will proceed if blood counts demonstrate ANC $\geq 1.5 \times 10^9/L$ and platelets $\geq 100 \times 10^9/L$ (See Table 2).

CONFIDENTIAL

STUDY DRUG(S): EVEROLIMUS
FINAL PROTOCOL DATE: 19 JUNE 2014

SCRI INNOVATIONS STUDY NUMBER: BRE 212
VERSION 1.0

Table 2 Everolimus Dose Modifications Due to Hematologic Toxicities

Toxicity	Actions
Grade 3 thrombocytopenia (platelets <50, $\geq 25 \times 10^9/L$)	Interrupt everolimus until resolution to \leq Grade 1. If AE resolution occurs \leq 7 days, reintroduce everolimus at the dose level prior to interruption. If AE resolution occurs $>$ 7 days, or event recurs within 28 days, reintroduce everolimus at one dose level lower, if available.
Grade 4 thrombocytopenia (platelets < $25 \times 10^9/L$)	Interrupt everolimus until recovery to \leq Grade 1. Then reintroduce everolimus at one dose level lower, if available.
Grade 3 Neutropenia (neutrophils $<1, \geq 0.5 \times 10^9/L$) or Grade 3 anemia (Hgb <8.0-6.5g/dL; <4.9-4.0 mmol/L; <80-65 g/L; transfusion indicated.)	Interrupt everolimus until resolution to \leq Grade 1 or baseline value. If AE resolution occurs \leq 7 days, reintroduce everolimus at the same dose level. If AE resolution occurs $>$ 7 days, or event occurs within 28 days, reintroduce everolimus at one dose level lower, if available.
Grade 4 Neutropenia (neutrophils $<0.5 \times 10^9/L$) or Grade 4 anemia (Life-threatening consequences; urgent intervention indicated.)	Interrupt everolimus until recovery to \leq Grade 1 or baseline value. Reintroduce everolimus at one dose level lower, if available.*
Febrile Neutropenia	Interrupt everolimus until resolution to \leq Grade 1 (or baseline value) and no fever. Reintroduce everolimus at one dose level lower, if available.*
Grade 3 AE recurrence after dose reduction	Interrupt everolimus until resolution to \leq Grade 1. Reduce dose to the next lower dose level, if available. The lowest possible dose level of everolimus is 5 mg every other day (2.5 mg daily). Below this level, everolimus must be discontinued.

*Grade 4 AE recurrence (including febrile neutropenia) after dose reduction, discontinue everolimus.

*Any hematologic toxicity requiring everolimus interruption for $>$ 28 days, discontinue everolimus.

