6.2 Everolimus Dose Modifications Due to Non-Hematologic Toxicity

Dose reductions and management of non-hematologic toxicities related to everolimus are defined in Table 3 and Table 4.

CONFIDENTIAL

STUDY DRUG(S): EVEROLIMUS
FINAL PROTOCOL DATE: 19 JUNE 2014

SCRI INNOVATIONS STUDY NUMBER: BRE 212
VERSION 1.0

Table 3 Everolimus Dose Modifications and Management of Hepatic Toxicity

Toxicity	Actions
AST or ALT elevation Grade 3 (> 5.0 - 20.0 ULN)*	Interrupt everolimus administration until resolution to \leq Grade 1 (or \leq Grade 2, if baseline values were within the range of Grade 2). If resolution occurs \leq 7 days, reintroduce everolimus at the dose level prior to interruption. If resolution occurs > 7 days, or if event recurs within 28 days, hold everolimus until recovery to \leq Grade 1 or baseline value and reintroduce everolimus at one dose level lower, if available.
AST or ALT elevation Grade 4 (> 20 x ULN)*	Interrupt everolimus administration until resolution to \leq Grade 1 (or \leq Grade 2, if baseline values were within the range of Grade 2). If resolution occurs \leq 7 days, reintroduce everolimus at one dose level lower. If resolution occurs > 7 days, discontinue everolimus.
Recurrence of Grade 4 after dose reduction or toxicity requiring Everolimus interruption for > 28 days	Discontinue everolimus.
Grade 3 or 4 clinical liver failure (asterixis or encephalopathy/coma)	Discontinue everolimus.

* Should HCV flare be confirmed, the guidelines for flare must take precedence (See Section 6.2.10).

CONFIDENTIAL

STUDY DRUG(S): EVEROLIMUS
FINAL PROTOCOL DATE: 19 JUNE 2014

SCRI INNOVATIONS STUDY NUMBER: BRE 212
VERSION 1.0

Table 4 Everolimus Dose Modifications and Management of Non-Hematologic Toxicity

Toxicity	Actions
Intolerable Grade 2 mucositis, or Grade 3 AE (except pneumonitis [see Table 5] and except hyperglycemia or hypercholesterolemia [See Section 6.2.5])	Interrupt everolimus administration until resolution to \leq Grade 1 or baseline value. If resolution occurs within \leq 7 days, reintroduce everolimus at the dose level prior to interruption. If resolution occurs $>$ 7 days, or if event recurs within 28 days, hold everolimus until recovery to \leq Grade 1 or baseline value and reintroduce everolimus at one dose level lower, if available. Patients will be withdrawn from the study if they fail to recover to \leq Grade 1 or baseline value within 28 days.

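### In Table 2, the Grade 3 neutropenia/anemia row can give two restart doses for one first event, because its 28-day trigger differs from the parallel rows and has no stated start; the printed anemia grades also leave a value without a clear row

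*Protocol*

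**What the plan says.** Protocol Section 6.1, Table 2, handles Grade 3 neutropenia and Grade 3 anemia in one row. Everolimus is interrupted until recovery. If recovery takes 7 days or less, the instruction is to "reintroduce everolimus at the same dose level". The next sentence covers recovery that takes more than 7 days, and adds a second trigger: "or event occurs within 28 days, reintroduce everolimus at one dose level lower, if available". The row does not say from which date the 28 days run.

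The Grade 3 thrombocytopenia row of the same table has the same structure, but its trigger reads "or event recurs within 28 days, reintroduce everolimus at one dose level lower, if available". In Section 6.2, the Grade 3 AST/ALT row of Table 3 and the Grade 3 row of Table 4 both read "or if event recurs within 28 days, hold everolimus until recovery to" Grade 1 or baseline, then restart one level lower.

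For anemia, the Grade 3 entry is "Grade 3 anemia (Hgb <8.0-6.5g/dL; <4.9-4.0 mmol/L; <80-65 g/L; transfusion indicated" and the Grade 4 entry is "Grade 4 anemia (Life-threatening consequences; urgent intervention indicated". Section 6 states the grading system: "All toxicities will be graded utilizing the NCI CTCAE v 4.0". Table 1 gives the dose levels as 10 mg daily, 5 mg daily and 5 mg every other day. Section 6 allows at most two reductions; a patient who needs a third must stop everolimus.

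**The concern.** *Recurs* carries its own reference point, because there must have been an earlier event. *Occurs* does not. With *occurs*, a patient's first Grade 3 neutropenia or anemia can satisfy the 28-day condition. If that event also clears within 7 days, the row tells the site both to keep the dose and to lower it.

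This is an operative dosing instruction. It decides the restart dose and whether one of the two permitted reductions is spent. It also feeds the analysis: SAP Table 5 tabulates patients by number of dose reductions, and SAP Table 10 counts adverse events that led to a reduction. Safety and tolerability is the secondary objective. With about nine sites, the same event could be handled and tabulated in two ways.

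The anemia definitions raise a smaller question of the same kind. The row a patient falls in determines the action, and the printed definitions of Grades 3 and 4 do not meet.

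**Working it through.** The plan states no figure on this point, so the check is a comparison of wording and a listing of cases.

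**Step 1. The 28-day trigger across the parallel Grade 3 rows**

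| Row | Trigger word | Implied start of the 28 days |
|---|---|---|
| Table 2, thrombocytopenia | recurs | an earlier event |
| Table 2, neutropenia/anemia | occurs | none stated |
| Table 3, AST/ALT | recurs | an earlier event |
| Table 4, Grade 3 event | recurs | an earlier event |

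One row of the four differs.

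**Step 2. A first Grade 3 neutropenia or anemia, read literally**

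| Resolution | Within the 28 days? | Instruction(s) met |
|---|---|---|
| 7 days or less | no | same level |
| more than 7 days | no | one level lower |
| more than 7 days | yes | one level lower (both triggers agree) |
| 7 days or less | yes | same level **and** one level lower |

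The instructions collide in one of the four combinations. If the row said *recurs*, a first event could not meet the 28-day condition, and the fourth line would not arise for it.

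**Step 3. How often the fourth line applies depends on the missing start date**

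- If the 28 days are the first 28 days of treatment, only events in that period are affected.
- If they are the current 4-week cycle (a possible reading, since Section 6.1 ties dose modification to Day 1 of each cycle), nearly every event falls inside.
- If they run from a previous event, no first event is affected.

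The row does not choose between these.

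**Step 4. Size for one patient**

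From Table 1, at the starting dose, the two readings are 10 mg and 5 mg daily: (10 − 5)/10 = 50% less under the lower one. The lower reading may also use one of the two permitted reductions.

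**Step 5. The anemia definitions**

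The platelet grades in Table 2 meet at 25 × 10⁹/L and the neutrophil grades at 0.5 × 10⁹/L. For anemia, the printed Grade 3 range ends at 6.5 g/dL and Grade 4 has clinical criteria only. A hemoglobin below 6.5 g/dL therefore maps as follows:

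- If it is life-threatening or needs urgent intervention, the Grade 4 row applies.
- If it is neither of these but transfusion is needed, the Grade 3 row applies only if the transfusion wording is read as a criterion on its own, although the value lies below the printed range.
- If none of these features is present, no printed row covers it.

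The choice of row matters. The Grade 4 row always restarts one level lower, if available, and its footnote stops everolimus on recurrence after a reduction. The Grade 3 row can return the patient to the same level.

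**The case against.** The strongest reply is that this is a one-word slip. The thrombocytopenia row, in the same table, supplies the sense, and reading *occurs* as *recurs* leaves every sentence with something to do. By contrast, if any 28-day window counts, every event qualifies and the same-dose sentence never operates alone, which is hardly a sensible reading. This has force: it makes a drafting slip a likely explanation. It does not settle the row. Reading the 28 days as early treatment also leaves both sentences with work to do. And if the second sentence is taken as an exception that overrides the first, there is no collision, but a first event in the window is then stepped down, unlike in the parallel rows. A site has to apply the row as printed.

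A second reply is that the conflict is narrow. That stands. A reader might infer that every first Grade 3 neutropenia or anemia receives two contradictory doses. The case listing shows it does not: three of the four combinations give one answer.

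A third reply concerns hemoglobin. A reader might infer that any value below 6.5 g/dL has no instruction. The documents do not support that: Grade 4 has no numeric limit and includes cases that need urgent intervention, and the Grade 3 entry mentions transfusion. Section 6 also places grading under CTCAE v4.0. Its anemia text is not reproduced in the documents, so whether it closes the remaining gap cannot be judged from them. What stands is that the printed rows do not meet.

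**Conclusion.** The point holds in a limited form. The Grade 3 neutropenia/anemia row is out of line with its three parallels. As printed, it gives two restart doses for a first event that resolves in 7 days or less and falls in a 28-day window with no stated start. For such a patient at the starting dose, the difference is 10 mg against 5 mg daily and possibly one of the two reductions. The conclusion rests on a literal reading of the row; no view is taken on which instruction was meant.

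The number of affected patients cannot be derived. A reader might take the 6% rate of Grade 3 or 4 anemia that Section 1.2 reports for the cited randomized trial and compute 0.06 × 46 = 2.8, about 3 patients. That is an expected count of all such anemia, not of patients who face the conflict. It includes Grade 4 events, which have their own row, and events that take more than 7 days to resolve, which get one answer. The documents give neither the share that resolves within 7 days nor a Grade 3 neutropenia rate. Section 6 does list neutropenia among the frequent laboratory abnormalities, but adds that most of the listed events were Grade 1 or 2.

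A reader might also infer that PFS is affected through exposure. Nothing in the documents shows this, and the sample size and the PFS analysis method are untouched. The consequences that can be shown are for dose handling and the tabulation of reductions.

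The anemia point is secondary: a hemoglobin below 6.5 g/dL that is neither life-threatening nor in need of urgent intervention has no clear printed row.

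**What to change.** The sponsor should:

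- reconcile the Grade 3 neutropenia/anemia row of Table 2 with the thrombocytopenia row and the Grade 3 rows of Tables 3 and 4, so that a single instruction applies to a first event that resolves in 7 days or less;
- state the date from which the 28 days run;
- reconcile the printed Grade 3 and Grade 4 anemia definitions with each other and with the CTCAE v4.0 grading named in Section 6, so that every hemoglobin value has one row;
- notify the sites.

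Which dose rule stands is a clinical decision for the study chair. The cost is a wording correction through the amendment process in Section 14.1 and a notice to sites. No assessment, sample size or analysis changes.
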